### Abstract

**Background:** Available therapeutic options for idiopathic fecal incontinence (FI) are limited and unsatisfactory. There are no controlled studies documenting the efficacy of medications used to treat FI. We observed that oral clonidine significantly reduced diarrhea in patients with urge FI; while clonidine reduced the frequency of FI, effects were not statistically significant. Small uncontrolled studies suggest that the bile acid binding resin colesevelam also improves functional diarrhea. However, there are no controlled studies that have investigated the effect of colesevelam in FI. In this placebo controlled study, we plan to investigate the effects of combining colesevelam with clonidine on symptoms in women with FI. The primary aim of our study is to investigate the hypotheses that compared to placebo, colesevelam and clonidine will reduce the frequency of FI and rectal urgency. Additionally, we will also investigate the stool and mucosa associated microbiota in these patients at baseline and after treatment. The role of microbiota in pathogenesis of FI is unknown and we hope this study will offer us valuable insight into this question. Sixty women (18-80 y) with symptoms of urge or combined (i.e. urge and passive) FI will be recruited to this study and treated with a combination of colesevelam and clonidine or placebo for 4 weeks. The primary outcome will be the proportion of patients who achieve at least 50% reduction in the frequency of FI (number of FI episodes per Diem) at the end of 4 weeks of treatment.

## **A. Specific Aims**

Fecal incontinence (FI) is a common symptom that can significantly impair quality of life. The current management of FI, particularly in patients with moderate to severe symptoms, is unsatisfactory. Our previous study showed that clonidine, a  $\alpha$ 2-agonist significantly decreased the proportion of loose stools in patients with urge or combined FI who also had diarrhea. While clonidine reduced the frequency of FI, effects were not statistically significant. A retrospective analysis of patients with bile acid malabsorption (BAM) observed that colesevelam, a bile acid binding resin improved subjective symptoms of FI in more than 70% patients. A prospective placebo controlled study on the impact of colesevelam in patients with FI is however lacking.

While BAM and alterations in fecal and colonic microbiota have been implicated to contribute to functional diarrhea and IBS respectively, the contribution of these disturbances to the pathogenesis or management of FI has not been evaluated. A better understanding of the same is necessary to guide the management of FI. Likewise, while IBS has been associated with gene polymorphisms, no studies have evaluated the association between gene polymorphisms and FI. Finally, the colonic mucosal microbiota are currently assessed by obtaining mucosal biopsies during a flexible sigmoidoscopy. It is conceivable that the mucosal microbiota can also be sampled with an rectal catheter. However, the characteristics of the colonic mucosal microbiota profile obtained with sigmoidoscopy and a catheter have not been compared.

The **central hypothesis** of this study is that a combination treatment with clonidine and colesevelam is better than placebo in reducing stool frequency and rectal urgency in FI. Additional hypotheses are that FI is associated with (i) BAM, (ii) alterations in the fecal and colonic mucosal microbiota, which are modified by treatment with colesevelam and clonidine and (iii) single nucleotide polymorphisms (SNPs) of selected genes.

In order to investigate these hypotheses we propose five aims as follows:

Aim 1: Compare the effects of combination treatment with colesevelam and clonidine vs. placebo on bowel symptoms in FI

Aim 2: Investigate the prevalence of BAM in patients with FI

Aim 3: Evaluate the fecal and colonic mucosal microbiota in patients with FI and the effects of treatment with colesevelam and clonidine

Aim 4: Compare the colonic mucosal microbiota obtained with mucosal biopsies during a flexible sigmoidoscopy and an rectal catheter in FI

Aim 5: Investigate SNPs associated with FI through microarray analysis of genomic DNA obtained at baseline.

## **B. Background and Significance**

Fecal incontinence, the involuntary leakage of stool from the anus, is a common symptom not only in nursing home residents, but also in the community. Our observations (2800 women) from Olmsted County demonstrate that one of 10 adult women and one of five women aged  $\geq 50$  years have had one or more episodes of FI, unrelated to an episode of acute diarrhea. Almost one of 15 adult women have moderate to severe FI.

There is very limited, mostly uncontrolled, evidence to support the approaches currently used to manage FI. Based on observations of responsiveness to placebo in controlled clinical trials, conservative measures (e.g., dietary modification, behavioral measures to suppress rectal sensation and not including biofeedback therapy) improved symptoms in approximately 25% of patients. Amitriptyline and loperamide improved diarrhea and rectal urgency in uncontrolled studies. However, the use of these agents

is often limited by constipation. Biofeedback therapy is better than pelvic floor exercises alone in patients who do not respond to conservative measures. In the only controlled clinical trial of medical therapy for FI, the effects of oral clonidine (0.1 mg twice daily) for 4 weeks on symptoms were not significantly different versus placebo in all comers with FI. However, clonidine significantly decreased the proportion of loose stools in FI patients with diarrhea. Among patients with diarrhea, clonidine decreased the proportion of days with FI; however results were not statistically significant. Uncontrolled studies suggest that the bile acid binding resin colesevelam also increased stool consistency in patients with functional diarrhea. A retrospective chart review and questionnaire suggested that colesevelam improved diarrhea and fecal incontinence in patients with cancer and diarrhea due to suspected bile acid malabsorption. However, among patients with functional diarrhea, the effects of bile acid binding agents on stool consistency were relatively modest. For example, in a study from Mayo Clinic, colesevelam reduced the Bristol score from an average of 4.8 before to 4.4 after therapy. While colesevelam increases stool consistency by binding bile acids, clonidine does so by improving net absorption of fluids and electrolytes. Clonidine can also increase rectal capacity and reduce rectal sensation. Therefore, we propose to compare the effects of a combination of colesevelam and clonidine to placebo on bowel symptoms in patients with urge or combined type of FI.

At present, FI is attributed to bowel disturbances, particularly diarrhea, and anorectal dysfunctions. Among older women with FI, our data strongly suggest that diarrhea and rectal urgency are more important risk factors than obstetric anal sphincter injury. Because many women with FI also have bowel disturbances (i.e., irritable bowel syndrome [IBS]), it is important to understand the contribution of peripheral dysfunctions (e.g., BAM, altered colonic microbiota), which are observed in IBS, to FI. For example, while several small studies observed differences in the microbiota in feces between health and irritable bowel syndrome, we recently observed major differences in the *mucosal* microbiota profile between healthy and constipated women. However, no studies have evaluated the fecal and colonic mucosal microbiota in FI. Currently, the mucosal microbiome is evaluated by obtaining mucosal biopsies during flexible sigmoidoscopy. It may be possible to assess the mucosal microbiota with an rectal catheter, which is a noninvasive technique. Hence, we propose to compare the fecal and colonic mucosal microbiota obtained with flexible sigmoidoscopy and an rectal catheter in patients with FI.

In the community, the prevalence of FI in men is similar to that in women (8.9% and 7.7% respectively). However, in our practice, a majority of patients with FI are women, who have had several vaginal deliveries. By contrast, the 3 main risk factors for FI in men are: proctitis secondary to radiotherapy for prostate cancer, a rectal evacuation disorder, and iatrogenic anal sphincter injury (e.g., due to surgery). Hence, the pathophysiology of FI is differs between men and women. Therefore, and to ensure a more homogenous composition of the patient group, this study is limited to women.

## **C. Research Design and Methods**

## 1. Overall experimental design.

This study will consist of four phases (Figure 1)

[figure not shown]
### 1. Phase 1 (Initial screening)

Patients who consent to participate in the study will visit with the investigator during which a physical examination may be performed. During this visit they will be asked to complete questionnaires designed

to determine whether or not they have FI, the type of FI, screen for anxiety or depression and assess quality of life at baseline. **Those who have diarrhea but not FI as assessed by the questionnaires (i.e. Bristol stool type 6 or 7, or >3 bowel movements/day on average) will be excluded from the study.** Eligible patients who give consent will undergo a urine pregnancy test, a 12 lead EKG, anorectal manometry (if not done at Mayo Clinic in the last 6 months), spot stool sample for microbiota analysis, blood draw for genotyping, assessment of the rectal mucosal microbiota with a rectal catheter, and an optional flexible sigmoidoscopy. Patients will be asked to record their dietary intake for 72 hours prior to collecting the stool sample.

Of these tests in phase 1, only the pregnancy test and EKG will determine whether patients proceed to phase 2. The remaining tests will be used to assess specific aims 2-5. Anorectal manometry will help clarify whether these patients have FI because of weakness of the anal sphincter or rectal hypersensitivity. The spot stool sample and rectal mucosal catheter will be used to assess the microbial diversity in FI. Among patients who have a flexible sigmoidoscopy, the mucosal microbiota will be compared on mucosal samples and a rectal catheter. In an attempt at (i) avoiding situations where we recognize subjects are not eligible to participate when they present at the screening visit and (ii) reduce the time taken for screening visits, we propose, when feasible, to ask participants to complete the questionnaires and a 2 week bowel diary before they come for their screening visit. Subjects will return these questionnaires to us by regular or electronic mail. If subjects are not subsequently consented/enrolled into the study, these items will be destroyed. [This bowel diary is identical to that approved for use later in the study.]

Figure 1. Study design

### 2. Phase 2 (Completion of bowel diaries)

Patients, who have FI, as documented by the questionnaire during phase 1, are not pregnant, and do not have EKG exclusion criteria documented below will enter phase 2. During this phase, patients will fill out daily bowel diaries to ascertain if they have FI symptoms of sufficient severity. The duration of this phase is variable and ranges from 2-4 weeks as clarified below. Only those patients who meet *all* the following criteria at the earliest weekly review of the bowel diaries starting at week 2 i.e., (i) completion of at least 5 out of 7 days of the diary in the preceding week and 10 out of 14 in the preceding 2 weeks, (ii) experience at least 1 episode of FI per week averaged over 2 weeks, (iii) have a Bristol stool form score  $\geq 3$ , and (iii) an average stool frequency of  $\geq 1$ /day will enter the treatment phase. Patients who have not filled out the minimum number of days of bowel symptoms will be asked to fill out bowel diaries for an additional 2 weeks. Those who satisfy criteria at the end

of the two additional weeks will proceed to Phase 3. Otherwise their participation in the trial will be terminated and they will exit the study.

### **3. Phase 3 (Treatment Phase)**

Patients who satisfy symptom criteria in Phase 2 will be randomized in a 1:1 ratio to receive either a combination of colesevelam (1.875 gm twice daily) and clonidine (0.1 mg oral twice daily) or an identical placebo for 4 weeks. The randomization, to be prepared by [name], will be balanced on age (<50 vs. ≥ 50 y) and BMI (<30 vs. ≥ 30 kg/m^2). Patients will fill *daily* bowel diaries for the entire duration of the treatment phase and mail them in every week. Patients will be contacted periodically (by phone or email) to assess compliance with medications, with filling bowel diaries and for any adverse events. At the end of the treatment phase, patients will be asked to fill questionnaires pertaining to their quality of life and satisfaction with treatment. During the treatment phase, patients will be allowed to use rescue medication in the form of loperamide to circumvent the potential for withdrawal from the study due to overwhelming symptoms. Patients are allowed to take loperamide (2mg/dose) up to 3 unit doses in a 24 hour period, 5 unit doses in a 48 hour period or 10 unit doses in any 7-day period. Patients will need to record their loperamide usage in the bowel diary.

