## **C. Phase 3**

### Inclusion criteria:

- (i) Completion of at least 5 out of 7 days of the diary in the preceding week and 10 out of 14 in the preceding 2 weeks
- (ii) At least 1 episode of FI per week averaged over 2 weeks
- (iii) Average Bristol stool score of 3 or higher
- (iv) Average stool frequency of  $\geq 1$ /day

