**Table 1. Symptom assessment tools and their administration during the study**

	Phase 1	Phase 2	Phase 3	Phase 4
Duration	Up to 1 week	2-4 weeks	4 weeks	4 weeks
Bowel questionnaire	X		X	X
Quality of life questionnaire	X		X	X
Hospital anxiety and depression questionnaire	X			X
Daily bowel diaries		X	X	X
Satisfaction with treatment			X	

4. Data and statistical analysis

i. Power Statement:

Based on the observed difference in the frequency of FI (i.e., mean number of FI episodes per subject per diem) between treatment and placebo groups in the clonidine study, we estimate that approximately 33 subjects in each treatment group (i.e. colesevelam and

clonidine vs placebo) will provide 80% power, using a two sided alpha level of 0.05, to detect at least a 50% difference in the frequency of FI between treatment groups.

ii. Data Analysis Plan:

a) Statistical analysis

An Excel (Microsoft, Redmond, WA) spreadsheet of treatment assignments (balanced on age and BMI) will be generated (by [name]) and sent to the research pharmacy. Study personnel will be blinded until the study is completed.

Bowel diaries will be analyzed as follows: Stool frequency, form, urgency and use of rescue medications will be averaged first for each day and then over 1-2 weeks (two weeks in Phase 1 and one week in Phase 3) in each subject.

We will compare response to treatment between colesevelam/clonidine and placebo between for the treatment period using the values during Phase 1 as covariates and separately, post-treatment. The analyses will use an  $\alpha$  value of 0.05 for each comparison. Treatment groups will be compared using analysis of covariance (ANCOVA) with the corresponding baseline (Phase 1) value as the covariate. Data will be analyzed per intent-to treat analysis using all subjects randomized. Missing values will be imputed as described previously and an adjustment in the ANCOVA error degrees of freedom will be made. Separate ANCOVA models will be used to evaluate whether treatment effects were influenced by the presence or absence of diarrhea at baseline. All tests will be two tailed.

Endpoints

The primary and secondary endpoints have been well described in our study of clonidine in FI and will be employed in this study as well

a) Primary endpoint:

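### Baseline diarrhea, the plan's own candidate effect modifier, is neither balanced at randomisation nor adjusted for in the main comparison, and the balancing factors age and BMI are not in the model either

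*Combined protocol and SAP*

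**What the plan says.** Under Phase 3 (Treatment Phase) in Section C.1, women are "randomized in a 1:1 ratio", with allocation "balanced on age (<50 vs. ≥ 50 y) and BMI". The statistical analysis text in Section C.4.ii repeats those two factors and adds no other.

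The same section compares arms by ANCOVA with the baseline value of the same endpoint as covariate. Diarrhea, age and BMI are not named as covariates. Further ANCOVA models are to "evaluate whether treatment effects were influenced by the presence or absence of diarrhea at baseline". No other baseline factor has an effect-modification analysis.

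Section B explains the interest in diarrhea. In the earlier clonidine trial, symptoms did not differ significantly from placebo overall, but "clonidine significantly decreased the proportion of loose stools in FI patients with diarrhea". Days with FI also fell in that subgroup, though not significantly. Section B also ranks diarrhea and rectal urgency above obstetric sphincter injury as risk factors in older women.

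Entry to Phase 3 requires "Average Bristol stool score of 3 or higher" and at least one stool a day on average, so women without diarrhea are admitted. The diary is reviewed before randomisation.

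On size, the Abstract gives "Sixty women (18-80 y) with symptoms of urge or combined" FI, while the power statement says "we estimate that approximately 33 subjects in each treatment group". Both are used below.

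**The concern.** A small trial should balance on, or adjust for, the baseline factors most likely to influence outcome. Here the factor with the best support in the plan's own background is left to chance in the allocation and left out of the main model. BMI is balanced, although the documents do not link it to FI or to response.

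The baseline covariate does not clearly close the gap. The Abstract's primary outcome is the proportion of women with at least a 50% fall in FI frequency. A responder status has no baseline value of its own, and no binary model is stated. As written, nothing adjusts the responder comparison for diarrhea.

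At stake is how far one result can be trusted. If the arms happen to differ noticeably in diarrhea, a reader will ask how much of the difference between them comes from case mix, and the plan holds no prespecified answer.

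**Working it through.** **Inputs.** From the documents: 1:1 allocation; 30 per arm (Abstract) or 33 per arm (power statement). Assumed: a diarrhea share of 30%, 40% or 50%, and a 30-point responder gap between women with and without diarrhea. Balancing on age and BMI is ignored in these calculations.

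**The plan's own figure.** The power statement says that 33 per arm "will provide 80% power, using a two sided alpha level of 0.05" for a 50% difference in FI frequency. It gives no mean, SD or responder rate, so the figure cannot be reproduced. Solved backwards for two means, d = (1.960 + 0.842) × √(2/33) = 0.69 SD. This serves as a yardstick below.

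**Step 1: chance imbalance.** With K women with diarrhea among 2n, the number X in the active arm is hypergeometric (2n, K, n). The imbalance is |2X − K|/n.

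| Per arm | Share | K | Smallest split of 20 points or more | Probability |
|---|---|---|---|---|
| 30 | 30% | 18 | 12 vs 6 | 15.8% |
| 30 | 40% | 24 | 15 vs 9 | 18.7% |
| 30 | 50% | 30 | 18 vs 12 | 19.6% |
| 33 | 30% | 20 | 14 vs 6 | 5.9% |
| 33 | 40% | 26 | 17 vs 9 | 7.7% |
| 33 | 50% | 33 | 20 vs 13 | 13.9% |

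The lower figures at 33 per arm partly reflect whole numbers: the first attainable imbalance past 20 points is 7/33 = 21 or 8/33 = 24 points.

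**Step 2: effect on the responder difference.** Take 15 vs 9 at 30 per arm, with the 15 on active treatment: 50% vs 30% diarrhea, 40% overall.
- Same 30-point gap in both arms (purely prognostic): 0.30 × (0.50 − 0.30) = 6 points.
- Gap on active treatment only (pure effect modification): 0.30 × (0.50 − 0.40) = 3 points, because only the active arm departs from the overall mix.

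The standard error of the crude difference is √(2p(1 − p)/30). It is 0.112 at p = 0.25 (the improvement rate with conservative measures in Section B, borrowed as a placebo rate) and 0.126 at p = 0.40 (assumed). Six points is therefore about half a standard error, and three points about a quarter.

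**Step 3: the same on a continuous scale, 33 per arm.** If diarrhea shifts the outcome by 0.3 to 0.8 SD (assumed), a 20-point imbalance moves the unadjusted difference by 0.20 × 0.3 = 0.06 to 0.20 × 0.8 = 0.16 SD. That is 9% to 23% of 0.69 SD, or 0.24 to 0.65 standard errors (√(2/33) = 0.246).

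**Step 4: error rates.** Simulation with a linear model, 33 per arm, 4,000 runs per scenario, total SD 1, 50% diarrhea unless stated:
- Type I error, allocation ignoring diarrhea: 0.049 to 0.050 unadjusted, 0.051 to 0.052 adjusted.
- Power at d = 0.69, allocation ignoring diarrhea: adjustment raises it from 0.80 to 0.81 if diarrhea shifts the outcome by 0.5 SD, and from 0.79 to 0.89 at 1 SD. If the effect instead differs by diarrhea (0.35 vs 1.03 SD), there is no gain (0.80 vs 0.79).
- With diarrhea in the model, balancing allocation on it adds almost nothing: 0.81 vs 0.81, and 0.89 vs 0.88.
- Balancing on a prognostic factor and then leaving it out of the model makes the test conservative: type I error 0.040 at a 0.5 SD shift and 0.022 at 1 SD. By the same logic, age and BMI belong in the model.

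**Step 5: the diarrhea analysis.** Unequal arms within the diarrhea subgroup cost 1% to 4% of efficiency on average (shares of 30% to 70%). Interaction power, for effects of 0.35 vs 1.03 SD, is 0.30 without and 0.28 with balancing at a 50% share, and 0.24 and 0.26 at 30%. These gaps are about the size of simulation error.

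**The case against.** The strongest reply is that nothing here is an error. Randomisation protects the test whether or not diarrhea is balanced, and simulated type I error stays near 0.05. A missing rationale for BMI is not a flaw. Adjusting for baseline FI frequency may absorb part of an imbalance, and for stool-form endpoints the baseline value bears directly on it. All of that stands, and it limits the point to a design improvement.

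A reader might infer three stronger claims that the documents do not support.

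- **That diarrhea governs response to clonidine.** The significant result in the previous clonidine trial concerns loose stools. The FI result in that subgroup was not significant, and no interaction test is reported. Section B also gives a rationale not tied to diarrhea, namely effects on rectal capacity and sensation, and this trial tests a combination.
- **That imbalance distorts the planned diarrhea analysis.** That analysis conditions on diarrhea, so a lopsided split costs a little precision and causes no bias. Its real limit is low power, which balancing does not change.
- **That BMI should give way to diarrhea in the allocation.** Once diarrhea is in the model, the swap gains almost no power.

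The reply does not cover the responder endpoint, for which no adjusted analysis is stated, or the absence of age and BMI from the model.

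**Conclusion.** The point holds as a low-cost improvement to the analysis plan. Diarrhea is singled out in the documents as a possible modifier and a main risk factor, yet it is neither balanced nor adjusted for, and the factors that are balanced are not in the model.

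The risk is moderate: a 20-point imbalance in roughly one trial in five to six at 30 per arm, and about one in seven to seventeen at 33. The resulting shift is 3 to 6 points in the crude responder difference, up to about half a standard error. These sizes rest on an assumed diarrhea share of 30% to 50% and an assumed 30-point responder gap. The upper end needs the same gap in both arms; the lower end applies if the gap exists only on active treatment. The consequence is lost precision and a result that is harder to defend after an unlucky draw, not an invalid test.

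**What to change.** Amend the statistical analysis text in Section C.4.ii as follows.

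1. Adjust the comparison of arms for baseline diarrhea (yes/no), age group and BMI group, in addition to the baseline value of the endpoint. For the responder endpoint, state the binary model. A logistic model with these terms would serve, reported with a standardised risk difference so that the result reads on the same scale as the crude one.
2. Define baseline diarrhea once, from the diary completed before randomisation, and use that definition both as covariate and in the diarrhea analysis. The plan now has no analysis definition. Phase 1 of Section C.1 describes diarrhea as Bristol 6 or 7 or more than three movements a day, in a questionnaire-based exclusion, whereas the secondary endpoints use Bristol 5 to 7. Name the diary explicitly: the analysis text calls baseline Phase 1, while Table 1 places the diaries in Phase 2.
3. Optionally, if the allocation list has not been issued, add diarrhea as a balancing factor and amend both places that list the factors. Removing BMI is not required.

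The data are already collected. The cost is a text change and a few model degrees of freedom. The optional step would add strata (eight with age and BMI kept, 2 × 2 × 2), which is thin for 60 to 66 women and another reason to put the covariate first.
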